6.8.2 Anti-diarrheal Medication During the First Cycle

All anti-diarrhea medication (including loperamide and any other concomitant medication for diarrhea) during the first cycle, will be listed to include the anti-diarrhea medication name and anti-diarrheal medication use duration.

6.8.3 Concomitant Therapy

Concomitant therapy will be listed.

6.9 Adverse Events (AEs)

AEs are graded by the investigators according to the NCI CTCAE v.4.0. AEs will be coded using MedDRA. Summaries will focus on treatment-emergent adverse events (TEAEs).

6.9.1 Treatment-emergent Diarrhea

Additional summaries will be provided for incidence of diarrhea by worst grade, and incidences of serious, treatment-related, and serious treatment related diarrhea, as well as the incidences of the action taken categories as a result of the diarrhea event, and the outcome of the last episode of diarrhea. The time to onset of first treatment emergent diarrhea, duration of treatment emergent diarrhea per episode and per patient and will be summarized. Same summaries will be repeated for grade 2 or higher diarrhea and grade 3 or higher diarrhea. The incidence of dose interruption due to diarrhea, dose reduction due to diarrhea and the number of dose interruptions and time to the first dose reduction and interruption will also be summarized.

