12.3.2. Secondary Endpoints

The secondary endpoints are the incidence and severity of diarrhea summarized according to the NCI-CTCAE version 4.0 in the first 28-day cycle of neratinib treatment and change from baseline at the time of the first colonoscopy (prior to initiation of therapy with neratinib) to the second study colonoscopy procedure in serological and fecal inflammatory markers. The primary analysis of the incidence and severity of diarrhea and inflammatory markers will be conducted after all patients have completed 2 colonoscopies and all samples have been collected and analyzed.

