2.2.2 Secondary Endpoints

The secondary endpoint will be the incidence and severity of diarrhea during the first 28-day cycle of neratinib monotherapy.

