3. DEFINITIONS

Baseline

The baseline value for a parameter of interest is the last measurement obtained prior to or on the date of the first dose of neratinib.

Cycle

The first cycle is 28 days for all subjects, all of whom receive neratinib and loperamide prophylaxis. After the first 28-day cycle, stage 1 to 3c breast cancer patients receiving extended adjuvant treatment return to clinic every 3 months. Metastatic breast cancer patients return to clinic at scheduled 21-day cycles, during with time they receive both neratinib and capecitabine.

Study Day 1

Study Day 1 is the date the first dose of neratinib is taken.

Treatment duration

Treatment duration in days = last dose date - first dose date + 1

Actual Dose Intensity

The actual dose intensity is defined as the cumulative actual dose divided by treatment duration.

Relative Actual Dose Intensity

The relative actual dose intensity is defined as the actual dose intensity divided by the planned dose intensity.

Prescribed Dose Intensity

The prescribed dose intensity is defined as the cumulative prescribed dose divided by treatment duration.

Treatment-Emergent Adverse Event (TEAE)

A TEAE is defined as an AE that occurs or worsens on or after the first administration of neratinib and up to 28 days after the second colonoscopy in patients with stage 1 to 3c breast cancer, and following completion of Cycle 2 in mBC patients.

Investigational Product (IP)

Investigational product (IP) is used to reference neratinib and capecitabine.

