9. LIST OF PLANNED TABLES, FIGURES, AND LISTINGS

9.1 TABLES

Tables
Summary of treatment-emergent diarrhea characteristics
TEAE (high-level summary)
TEAE by SOC, PT, and Grade
Grade 3 or 4 TEAE by SOC, PT, and Grade
Fatal TEAE by SOC, PT, and Grade
TEAE in descending order of incidence by PT
Grade 3 or 4 TEAE in descending order of incidence by PT
Fatal TEAE in descending order of incidence by PT
AESI by event category, PT, and Grade
Incidence of liver function test abnormality

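### SAP 6.9.1 summarizes diarrhea over the TEAE window and does not carry the protocol's first-cycle window into the secondary endpoint

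*SAP*

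**What the plan says.** SAP 2.2.2 defines the endpoint: "The secondary endpoint will be the incidence and severity of diarrhea during the first 28-day cycle of neratinib monotherapy". Protocol 12.3.2 names the matching summary: "the incidence and severity of diarrhea summarized according to the NCI-CTCAE version 4.0 in the first 28-day cycle of neratinib treatment".

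The SAP's analysis text is in 6.9.1, under a parent section (6.9) that directs its summaries at TEAEs. It says "Additional summaries will be provided for incidence of diarrhea by worst grade" and later adds "Same summaries will be repeated for grade 2 or higher diarrhea and grade 3 or higher diarrhea". Neither sentence mentions Cycle 1. The one diarrhea-specific entry in SAP 9.1 is "Summary of treatment-emergent diarrhea characteristics".

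SAP section 3 sets the TEAE window from the first neratinib dose "up to 28 days after the second colonoscopy in patients with stage 1 to 3c breast cancer, and following completion of Cycle 2 in" metastatic (mBC) patients.

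Elsewhere the SAP does state a first-cycle limit. Section 6.8.1 covers loperamide in the first cycle, and 6.8.2 covers "All anti-diarrhea medication (including loperamide and any other concomitant medication for diarrhea) during the first cycle". SAP section 8, on changes to the protocol's analyses, is marked not applicable.

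**The concern.** A programmer who follows SAP 6.9.1 literally will report diarrhea over a window about twice as long as the endpoint's. The added time also differs in kind. After Day 28 loperamide goes from scheduled to as needed (SAP 2.3.3), and mBC patients start capecitabine in Cycle 2 (SAP 2.3.5), so their later time is not monotherapy.

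The table can also change between the two analyses. The primary analysis is triggered by the last second colonoscopy (SAP 6), when the last patient's TEAE window may still be open.

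SAP 2.1.1 says the primary objective is not addressed in this SAP. First-cycle diarrhea is therefore the only endpoint in SAP 2.2 that the SAP itself has to deliver. With 3 to 5 patients, moving one patient across the boundary changes an incidence by 1/5 = 20 to 1/3 = 33 percentage points, so the counting rule should be settled before the data are seen.

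**Working it through.** The plan gives no figure for the length of the diarrhea window, so there is none to reproduce. The check is day arithmetic with Day 1 as the first neratinib dose.

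**Inputs**
- Endpoint window: Day 1 to 28 (SAP 2.2.2, Protocol 12.3.2).
- Second colonoscopy: Day 30 ± 3, i.e. Day 27 to 33 (SAP 2.3.1).
- Second colonoscopy in mBC, alternative timing: Day 1 of Cycle 2 plus up to 5 days, i.e. Day 29 to 34 (Protocol Appendix 1, Table A1.2, footnote o). The two mBC timings differ and must be reconciled; both are carried here.
- Cycle 2 in mBC: 21 days, starting after the second colonoscopy (Table A1.2, footnote a) and after a complete 28-day Cycle 1 (Protocol 6.1), so not before Day 29.
- Assumption: Cycle 2 starts on the colonoscopy day or the next day, subject to that Day 29 floor.

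**Stage 1 to 3c:** window end = colonoscopy day + 28.
- 27 + 28 = Day 55; 33 + 28 = Day 61.
- Beyond Day 28: 55 − 28 = 27 to 61 − 28 = 33 days.
- Share of the window outside the endpoint: 27/55 = 49% to 33/61 = 54%.

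**mBC:** window end = Cycle 2 Day 1 + 20.
- Day 30 ± 3: earliest 29 + 20 = Day 49; latest 34 + 20 = Day 54.
- Table A1.2 timing: earliest 29 + 20 = Day 49; latest 35 + 20 = Day 55.
- Together: Day 49 to 55, which is 21 to 27 days beyond Day 28.
- Share outside the endpoint: 21/49 = 43% to 27/55 = 49%.

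**Difference between settings for the same colonoscopy day**
- Day 27: 55 − 49 = 6 days longer in stage 1 to 3c.
- Day 28: 56 − 49 = 7 days.
- Day 29 or later: 28 − 21 = 7 days (next-day start) or 28 − 20 = 8 days (same-day start).

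These are lengths of observation, not effects. The documents give no probability that a first or worst diarrhea event falls after Day 28. Protocol 2.3.1.1 puts typical onset at 2 to 8.5 days across earlier neratinib studies, and 2.3.4.1 says Grade 3 diarrhea peaks in the first month. Both point to a small shift.

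**The case against.** The strongest reply is that Protocol 12.3.2 already plans the first-cycle summary. SAP section 1 says the SAP supplements the protocol's statistical section, and section 8 declares no change, so the protocol's window could be taken to govern still. This stands in part. A reader might infer that the endpoint has no planned summary anywhere, and the documents do not support that. What remains is that the SAP's methods text and table list, which drive programming, do not carry the window over.

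A reader might also treat the lack of a first-cycle diarrhea output in SAP 9 as proof of omission. That list is not exhaustive. It leaves out the medical history listing (6.4), the anti-diarrheal listing (6.8.2), and the treatment-related and serious TEAE tables (6.9.2). The point rests instead on the heading and text of 6.9.1, set against 6.8.1 and 6.8.2.

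The consequence is also limited. The Protocol Synopsis makes listings and narratives the main presentation, there is no test or threshold, and no comparison between settings is planned. First-cycle events in 3 to 5 patients could be counted from the TEAE listing, and the planned time-to-onset summaries would help show whether the two windows agree. This stands as a limit on severity. It is not a full answer, because the SAP does not say that the listing shows onset dates or dated grade changes, and it has no rule for an episode that crosses Day 28.

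**Conclusion.** The point holds in limited form. As written, SAP 6.9.1 and its one diarrhea table measure treatment-emergent diarrhea to Day 55 to 61 in stage 1 to 3c and about Day 49 to 55 in mBC, whereas the endpoint stops at Day 28. The mBC range rests on Cycle 2 not starting before Day 29 and on its starting on the colonoscopy day or the day after.

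The TEAE definition itself follows Protocol 12.3, and the table is correctly titled for what it contains. The fault is that it does not match the endpoint.

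A reader might infer that the reported incidence will be materially inflated. The documents do not support this: the background data suggest early onset, and no late-onset rate is given. Those data come from other regimens, however. The Study 6201 table is captioned as prophylaxis in months 1 and 2, while scheduled loperamide here ends at Day 28. The shift is therefore expected to be small but is not quantified. No data are lost. Severity is minor to should-fix.

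**What to change.** In SAP 6.9.1 and 9.1, add one table labelled as the secondary endpoint: diarrhea incidence by worst investigator-assigned CTCAE v4.0 grade, for events starting or worsening on Study Day 1 to 28 and before any capecitabine. Keep the TEAE-window table as supportive.

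Add a short derivation rule:
- An episode that crosses Day 28 is counted, with its worst investigator grade dated on or before Day 28.
- If the grade change is undated, query the investigator, with the Cycle 1 diary as support only, and flag the episode.
- Do not derive the grade from diary stool counts alone. Grading belongs to the investigator (SAP 6.9), and Grade 3 also covers incontinence, indicated hospitalization and limits on self-care (Protocol Appendix 2, Table A2.2).

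The cost is one small table and a few lines of SAP text. No new data collection is needed, since adverse events are monitored past Day 28 in both settings (Protocol Appendix 1, footnotes to Tables A1.1 and A1.2). The diary is already kept for Cycle 1, at most 3 × 28 = 84 to 5 × 28 = 140 diary days, and only ambiguous episodes would need checking.

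Two minor clarifications are separate from this point. The primary-analysis cut-off should allow for a second colonoscopy on Day 27, before the endpoint window closes. The mBC clause of the SAP's TEAE definition should state its end, as Table A1.2 does with the end of Cycle 2.

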6.9.2 Treatment-Emergent Adverse Events (TEAEs)

A high-level summary of TEAE will be provided and select summaries of TEAE subgroups (indicated in parentheses).

TEAEs will also be presented in incidence tables by system organ class (SOC), preferred term (PT), and grade for the following:

- Any TEAE (summary)
- Treatment-related TEAE
- Serious TEAE
- Serious treatment-related TEAE
- Grade 3 or 4 TEAE (summary)
- Fatal TEAE (summary)
- TEAE leading to dose reduction
- TEAE leading to dose interruption
- TEAE leading to treatment discontinuation

Incidence tables of TEAEs in descending order of frequency by PT will be presented for any TEAE, Grade 3 or 4 TEAE, and fatal TEAE.

Listings will be provided for SAEs, TEAEs, and TEAEs leading to study drug discontinuation.

6.9.3 Adverse Events of Special Interest (AESI)

The AESI for neratinib will be based on SMQ or the complete list of the Sponsor-defined group of PTs. Tables will be provided with a summary of the incidence of all AESI by PT and Grade.

6.9.4 Death

If applicable, deaths will be listed with the following variables: indicator of death (yes/no), on-study deaths (within 28 days after last dose of neratinib) (yes/no), and cause of death.

6.10 Clinical Laboratory Parameters

Laboratory data will be listed by visit/collection timepoint.

Listings of laboratory values for blood chemistry parameters and hematology parameters will be provided.

In addition, abnormalities in liver function tests will be listed.

6.11 Vital Signs

Vital sign measures (systolic and diastolic blood pressure, pulse, respiratory rate, oral temperature and weight) will be listed.

6.12 ECG Abnormality

Electrocardiograms (ECGs) are measured after resting in a supine position for 5 minutes and include Heart rate, Rhythm pattern, RR interval, PR interval, QRS interval, QT interval, QT_c interval-Bazett's, QTc interval-Fridericia's, QTc interval-Other. Overall evaluation is also indicated.

A listing of ECGs will be provided.

6.13 Left Ventricular Ejection Fraction (LVEF)

LVEF data will be listed.

6.14 Disease Recurrence

Disease recurrence data will be listed.

7. INTERIM ANALYSES

Not applicable

8. CHANGES TO THE ANALYSES PLANNED IN THE PROTOCOL

Not applicable

9. LIST OF PLANNED TABLES, FIGURES, AND LISTINGS

9.1 TABLES

Tables
Summary of treatment-emergent diarrhea characteristics
TEAE (high-level summary)
TEAE by SOC, PT, and Grade
Grade 3 or 4 TEAE by SOC, PT, and Grade
Fatal TEAE by SOC, PT, and Grade
TEAE in descending order of incidence by PT
Grade 3 or 4 TEAE in descending order of incidence by PT
Fatal TEAE in descending order of incidence by PT
AESI by event category, PT, and Grade
Incidence of liver function test abnormality

9.2 LISTINGS

Listings
Listing of disposition
Listing of deviations

Listing of demographics
Listing of cancer history
Listing of prior anti-cancer medications
Listing of serological parameters
Listing of stool parameters
Listing of neratinib exposure
Listing of capecitabine exposure
Listing of loperamide exposure
Listing of concomitant therapy
Listing of SAEs
Listing of TEAEs
Listing of TEAEs leading to IP discontinuation
Listing of deaths
Listing of laboratory values, blood chemistry
Listing of laboratory values, hematology
Listing of liver function test values
Listing of ECGs
Listing of Vital Signs
Listing of LVEF
Listing of disease recurrence

